## 12.2 Appendix 2 - SI units and conversion factors

Unit	Parameters
$10^{12}/\text{L}$	RBC count
g/L	Hemoglobin
$10^9/\text{L}$	WBC count, neutrophils, lymphocytes, basophils, eosinophils, basophils, monocytes, platelet count
IU/L	ALT, AST, ALP, LDH
$\mu\text{mol}/\text{L}$	Total bilirubin, creatinine
mL/min	Creatinine clearance
mmol/L	Sodium, potassium, magnesium, bicarbonate, glucose

Bilirubin (584.7 g/mol): <https://pubchem.ncbi.nlm.nih.gov/compound/5280352>

$$\begin{aligned}
 1 \text{ mg/dL} &= (0.01 \text{ g/L}) \times (1/584.7 \text{ mol/g}) \\
 &= 0.01/584.7 \text{ mol/L} \\
 &= 10000/584.7 \mu\text{mol/L} \\
 &= 17.10 \times 1 \mu\text{mol/L}
 \end{aligned}$$

Glucose (180.16 g/mol): <https://pubchem.ncbi.nlm.nih.gov/compound/79025>

$$\begin{aligned}
 1 \text{ mg/dL} &= (0.01) \text{ g/L} \times (1/180.16) \text{ mol/g} \\
 &= 0.01/180.16 \text{ mol/L} \\
 &= 10/180.16 \text{ mmol/L} \\
 &= 0.055506 \text{ mmol/L}
 \end{aligned}$$

Sodium (22.989769 g/mol): <https://pubchem.ncbi.nlm.nih.gov/compound/Sodium>

$$\begin{aligned}
 1 \text{ mg/dL} &= (0.01) \text{ g/L} \times (1/22.989769) \text{ mol/g} \\
 &= 0.01/22.989769 \text{ mol/L} \\
 &= 10/22.989769 \text{ mmol/L} \\
 &= 0.43497610 \times 1 \text{ mmol/L}
 \end{aligned}$$

Potassium (39.098 g/mol): <https://pubchem.ncbi.nlm.nih.gov/compound/Potassium>

$$\begin{aligned}
 1 \text{ mg/dL} &= (0.01) \text{ g/L} \times (1/39.098) \text{ mol/g} \\
 &= 0.01/39.098 \text{ mol/L} \\
 &= 10/39.098 \text{ mmol/L} \\
 &= 0.25577 \times 1 \text{ mmol/L}
 \end{aligned}$$

Magnesium (24.305 g/mol): <https://pubchem.ncbi.nlm.nih.gov/compound/magnesium>

$$1 \text{ mg/dL} = (0.01) \text{ g/L} \times (1/24.305) \text{ mol/g}$$

$$\begin{aligned}
 &= 0.01/24.305 \text{ mol/L} \\
 &= 10/24.305 \text{ mmol/L} \\
 &= 0.41144 \times 1 \text{ mmol/L}
 \end{aligned}$$

Bicarbonate (61.017 g/mol): <https://pubchem.ncbi.nlm.nih.gov/compound/Bicarbonate>

$$\begin{aligned}
 1 \text{ mg/dL} &= (0.01) \text{ g/L} \times (1/61.017) \text{ mol/g} \\
 &= 0.01/61.017 \text{ mol/L} \\
 &= 10/61.017 \text{ mmol/L} \\
 &= 0.16389 \times 1 \text{ mmol/L}
 \end{aligned}$$

Creatinine (113.12 g/mol): <https://pubchem.ncbi.nlm.nih.gov/compound/588>

$$\begin{aligned}
 1 \text{ mg/dL} &= (0.01) \text{ g/L} \times (1/113.12) \text{ mol/g} \\
 &= 0.01/113.12 \text{ mol/L} \\
 &= 10000/113.12 \text{ } \mu\text{mol/L} \\
 &= 88.402 \times 1 \text{ } \mu\text{mol/L}
 \end{aligned}$$

Summary of conversion factors when molecular weight is needed:

Parameters	Units	Conversion factor
Total Bilirubin	mg/dL to $\mu$ mol/L	17.10
Creatinine		88.402
Sodium	mg/dL to mmol/L	0.43497610
Potassium		0.25577
Magnesium		0.41144
Bicarbonate		0.16389
Glucose		0.055506

Trivial conversion into SI units using factor of 10 (e.g. conversion of mg/dL to mg/L) are not detailed but will be performed

### 12.3 Appendix 3 - Laboratory parameters graded according to CTCAE v5.0

Lab Test Name	SI Unit	CTCAE v5.0 – AE Term for decreased	CTCAE v5.0 – AE Term for increased
Hemoglobin	g/L	Anemia	Hemoglobin Increased
Leukocytes	10  /L	White blood cell decreased	Leukocytosis
Neutrophils	10  /L	Neutrophil count decreased	
Lymphocytes	10  /L	Lymphocyte count decreased	Lymphocyte count increased
Platelets	10  /L	Platelet count decreased	
Glucose	mmol/L	Hypoglycemia	Hyperglycemia
Alanine aminotransferase	IU/L		Alanine aminotransferase increased
Aspartate aminotransferase	IU/L		Aspartate aminotransferase increased
Total Bilirubin	µmol/L		Blood bilirubin increased
Alkaline phosphatase	IU/L		Alkaline phosphatase increased
Creatinine	µmol/L		Creatinine increased
Magnesium	mmol/L	Hypomagnesemia	Hypermagnesemia
Potassium	mmol/L		Hyperkalemia
Sodium	mmol/L	Hyponatremia	hypernatremia

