###### Laboratory abnormalities

The summaries will include all laboratory assessments collected from baseline assessment until 30 days after treatment discontinuation. All laboratory assessments will be listed and those collected during 30 days after study treatment discontinuation will be flagged in the listings.

All laboratory values will be converted into SI units and will have a severity grade calculated using appropriate common terminology criteria for AEs (NCI-CTCAE, version 5). A listing of laboratory values will be provided by laboratory parameter and patient. A separate listing will display notable laboratory abnormalities (i.e., newly occurring CTCAE Grade 3 or 4 laboratory toxicities). The frequency of these notable laboratory abnormalities will be displayed by parameter. The shift tables using CTCAE grades to compare baseline to the worst post-baseline value will be produced for all relevant safety measures as described in the statistical analysis

plan. Note that for parameters with two directions abnormalities (hypo/hyper), two tables will be presented.

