**Planned Dose intensity ( $10^8$  pfu/week):**

If last dose before D43 visit (visit day  $<$  42): 1

If last dose on or after D43 visit (visit day  $\geq$  42):

Given xx the theoretical study day of visit Dxx

$$\frac{6 + \text{Int}\left[\frac{(xx - 1 + 21 - 7 \times 6)}{21}\right]}{(\text{Last dose date} - \text{1st dose date} + 21)/7}$$

For example, at visit D85; then number of injections should be:  $6 + \text{int}((85-1+21-42)/21) = 9$

**Duration of exposure (weeks):** (Last dose date-1st dose date + 1)/7

All laboratory parameters will be expressed in the International System (SI) of units and the intensity grade using CTCAE version 5. A grade of 0 will be assigned when the value is within normal limits. In the case a local laboratory normal range overlaps into the higher (i.e., non-zero) CTC grade, the laboratory value will still be taken as within normal limits and assigned a CTC grade of 0. When normal limits are missing and needed for intensity grade determination, the grade will be set at missing. If normal limits are missing but not needed, grade intensity will be calculated as usual with CTCAE ranges.

Laboratory values recorded as “value  $<$  x” or “value  $>$  x” will be handled as the formula:

- $x = x * \sum_{i=1}^{n+2} (9 * 10^{-i})$  if value recorded as “value  $<$  x” with n denoted the number of significant digits
- $x = x * (1 + 10^{-n+2})$  if value recorded as “value  $>$  x” with n denoted the number of significant

digits

for the calculation of descriptive parameters and for the value derived in standard units. Other methods could be investigated for specific parameters. In individual listings, they will be presented as “< x” or “> x”.

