### 8.10.2 Laboratory abnormalities

The summaries will include all laboratory assessments collected from baseline assessment until 30 days after treatment discontinuation. All laboratory assessments will be listed and those collected more than 30 days after study treatment discontinuation will be flagged in the listings.

All laboratory values will be converted into SI units and will have a severity grade calculated using appropriate common terminology criteria for AEs (NCI-CTCAE, version 5). A listing of laboratory values will be provided by laboratory parameter and patient. A separate listing will display notable laboratory abnormalities (i.e., newly occurring CTCAE Grade 3 or 4 laboratory toxicities). The frequency of these notable laboratory abnormalities will be displayed by parameter. The shift tables using CTCAE grades to compare baseline to the worst post-baseline value will be produced for all relevant safety measures as described in the statistical analysis plan. Note that for parameters with two directions abnormalities (hypo/hyper), two tables will be presented.

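### SAP Appendix 3 gives potassium no decreased CTCAE term, in conflict with the SAP and protocol text that grades all laboratory values and promises two tables for parameters that can be low or high

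*SAP*

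**What the plan says.** Protocol 9.4.1 (Laboratory abnormalities) sets the rule: "All laboratory values will be converted into SI units and will have a severity grade calculated" under NCI-CTCAE version 5. SAP 8.10.2 repeats it. Both sections also plan three outputs:

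- a separate listing of newly occurring grade 3 or 4 results;
- a count of them: "The frequency of these notable laboratory abnormalities will be displayed by parameter";
- shift tables from baseline to worst grade, with the note that "for parameters with two directions abnormalities (hypo/hyper), two tables will be presented".

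SAP 7.6.2 says that laboratory parameters receive a CTCAE version 5 grade and adds: "A grade of 0 will be assigned when the value is within normal limits". Where normal limits are missing but not needed, the grade is to be derived from the CTCAE ranges in the usual way.

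SAP 10.1 lists the matching outputs: Table 14.3.4.1 (grade 3-4 listing) and Table 14.3.4.2.2 (biochemistry shift table). It shows no separately numbered table for the frequency by parameter.

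SAP Appendix 3 (section 12.3), headed "Laboratory parameters graded according to CTCAE v5.0", has one column for decreased terms and one for increased terms. Magnesium has "Hypomagnesemia" and sodium has "Hyponatremia" in the decreased column, each paired with an increased term. Potassium has only "Hyperkalemia".

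**The concern.** Potassium is in the biochemistry panel throughout treatment (protocol 6.2.1), and SAP Appendix 2 gives it an SI conversion factor. The values will exist in the right unit, but the appendix supplies no term against which to grade a low one. SAP 7.6.2 does not fill the gap, because its grade 0 rule covers only values within normal limits.

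Safety is the primary objective. Protocol 8.2.5 sends laboratory results to the adverse event form on clinical significance: symptoms, a change in study medication, or a need for treatment or management. The graded laboratory outputs are therefore where severity is shown by grade alone. If low potassium is never graded, those outputs say nothing about it, and a reader could mistake that for an absence of low values. Protocol 1.5.2 names nausea and vomiting among the common related events of this vector class, which makes low potassium plausible. That link is an inference; the protocol does not mention potassium there.

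**Working it through.** The plan gives no figure of its own to reproduce. The check is a reading of Appendix 3 against the body text, with a count of what is affected.

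**1. Directions in Appendix 3.** Hemoglobin 2, leukocytes 2, neutrophils 1, lymphocytes 2, platelets 1, glucose 2, ALT 1, AST 1, total bilirubin 1, alkaline phosphatase 1, creatinine 1, magnesium 2, potassium 1, sodium 2.

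- Tests: 14. Directions: 6 × 2 + 8 × 1 = 20.
- Rows in mmol/L: glucose, magnesium, potassium, sodium. Three have both directions; potassium alone has one.

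**2. Body text against appendix, for a potassium value below the normal range.**

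- By SAP 7.6.2, SAP 8.10.2 and protocol 9.4.1, the value is graded. If potassium counts as a parameter with both directions, it gets two shift tables.
- By Appendix 3 taken literally, there is no term for a low value, so no low-side grade is derived. The value cannot then qualify for the grade 3-4 listing, be counted in the frequency by parameter, or appear in a low-potassium shift table.

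The two readings give different outputs, and the SAP does not say which prevails.

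**3. Scheduled results affected.** Inputs: the biochemistry schedule in protocol Appendix II-B and its footnotes, and 20 injections.

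- D8 to D43, weekly: 6.
- D64, 85, 106, 127, 148, 169, 190: 7.
- Every 12 weeks after that: D190 + 84 = D274, so 1. The next would be D358. D43 is the 7th injection, so the 20th falls on 43 + 13 × 21 = D316, before D358.
- End of treatment: 1.
- Total per full course: 6 + 7 + 1 + 1 = 15.

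Six patients were treated (SAP 4), so the scheduled total is at most 15 × 6 = 90. The three run-in patients contribute 6 × 3 = 18 up to D43. Early stopping lowers these totals and unscheduled draws raise them. They count results, not abnormal results.

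**4. Illustration only.** The documents give no rate of low potassium. If a proportion p of patients had a newly occurring grade 3-4 low value, the chance that at least one of six did is 1 − (1 − p)^6:

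- p = 1%: 1 − 0.99^6 = 5.9%
- p = 5%: 1 − 0.95^6 = 26.5%
- p = 10%: 1 − 0.90^6 = 46.9%

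The three rates are assumptions. The results do not allow for capture on the adverse event form, so they overstate what would be missing from the report as a whole.

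**The case against.** The strongest reply is that the body text controls. The SAP body never cites Appendix 3 as the governing or complete grading specification. SAP 7.6.2 and 8.10.2 point to CTCAE version 5 itself, and a programmer who follows them would grade low potassium. Appendix 3 is not a full map of the panel either: bicarbonate is measured and has a conversion factor, but has no row. This stands in part. A reader might infer that low potassium cannot be graded under this plan. The documents do not support that; the omission follows only if Appendix 3 is programmed literally. What remains is a plan that gives two answers for a parameter it did select for grading.

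SAP 8.10.2 also limits shift tables to relevant measures described in the SAP. On that view Appendix 3 makes potassium one-directional and no second table was promised. This is arguable, but the SAP gives no reason for treating potassium differently from sodium and magnesium.

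The reply on consequences is stronger. Every potassium value is in Listing 16.2.8.2. A low value with symptoms, a change in study medication or a need for management is recorded as an adverse event (protocol 8.2.5) and graded by CTCAE (protocol 8.2.2.4). It then appears in Table 14.3.1.3, and in Table 14.3.2.5 if it is grade 3 or 4. Reviewers of the draft outputs (SAP 7.5 and 8.1) could also notice that the low block is absent. All of this stands and limits the point to graded laboratory outputs.

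**Conclusion.** Appendix 3 and the body text disagree on low potassium, and the disagreement lies in an operative specification for the safety outputs. Followed literally, Appendix 3 leaves a newly occurring grade 3-4 low potassium out of Table 14.3.4.1, the frequency by parameter and Table 14.3.4.2.2. The severity is minor: six treated patients, a descriptive analysis, and no raw data lost. The value that would go ungraded throughout is a grade 3-4 result that never reaches the adverse event form, and it would still be listed.

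Two stronger inferences should be resisted. One is that a dose-limiting toxicity could be missed. Dose-limiting toxicity and discontinuation are decided on adverse events (protocol 4.3.2 and 8.2.2.1), which Appendix 3 does not touch. The other is that the 5.9%, 26.5% and 46.9% figures estimate loss from the report. They rest on assumed rates and ignore adverse event capture.

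The conclusion rests on two assumptions. The first is that CTCAE v5.0 grades low potassium; the sodium and magnesium rows suggest so, but its text is not in the documents. The second is that the blank is in the source table rather than lost when the file was read. The row keeps an empty decreased cell in the same form as the ALT, AST and bilirubin rows, so a true blank is more likely, though not verified.

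**What to change.** In SAP Appendix 3, enter Hypokalemia in the decreased column of the potassium row. Add a low-potassium block to Table 14.3.4.2.2, and include low values in Table 14.3.4.1 and in the frequency of notable abnormalities by parameter. If the omission is deliberate, state that in the SAP with the reason.

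The cost is one table cell, one extra shift-table block and a rerun of the draft outputs. The potassium values and their SI conversion are already planned. The protocol, patients, visits and timing are unaffected.

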#### 6.2.1. Evaluation description

The following parameters will be measured during this period:

- **Inclusion/exclusion criteria**

Patient eligibility is to be established by the investigator by confirming that all the treatment period inclusion / exclusion criteria are met. Deviation from any eligibility criterion excludes a patient from registration into the treatment period.

- **Current medical conditions**

- Syndrome/pathology with established diagnosis starting during the screening period either recovered or ongoing
- “Signs and symptoms” symptoms with no associated syndrome (e.g., diarrhea) see section 8.2

- **Clinical evaluation**
  - Physical examination of major organ systems, including vital signs (body temperature, pulse rate and blood pressure) and weight
  - PS on ECOG scale (see APPENDIX I)
- **Concomitant medications and significant non-drug therapies**
- **Electrocardiogram (12 leads)**
  - At baseline, every 3 weeks for the first 6 weeks and then every 6 weeks up to Day 169, thereafter every 12 weeks, and at the end of treatment visit
- **Safety assessments**
  - AEs/SAEs collection see section 8.2
  - Follow-up of all ongoing AEs
- **Laboratory assessments**
  - CBC including RBC, Hb, WBC and differential, platelets
  - Biochemistry including AST, ALT, alkaline phosphatases, total bilirubin, glucose, electrolytes (sodium, potassium, magnesium and bicarbonates), creatinine and creatinine clearance
- **Blood sampling and cytapheresis** for translational research; if the post-baseline cytapheresis procedure is not clinically feasible, it can be replaced by a 150 ml blood draw.

**CA-125 evaluation** in an accredited central laboratory, serum concentration will be assessed every 3 weeks

- **Tumor imaging**
  - A CT-Scan of the pelvis and abdomen (or MRI) and X-ray or preferably CT-scan of the chest will be performed within 21 days prior to treatment initiation, on Day 43 and then every 9 weeks with a time window of +/- 7 days until disease progression justifying initiation of further treatment

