## **7 STATISTICAL DESIGN**

### **7.1 Sample size determination**

No formal sample size calculation is planned for this study.

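### SAP Appendix 3 gives potassium a high-side grading term but no low-side one, which conflicts with the two-direction rule in SAP 8.10.2

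*SAP*

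**What the plan says.** SAP section 12.3 is titled "Laboratory parameters graded according to CTCAE v5.0". It lists each test with its SI unit, a column headed "CTCAE v5.0 – AE Term for decreased" and a matching column for increases. In the potassium row the first of these columns is empty and the second reads "Hyperkalemia". The row above (magnesium) has "Hypomagnesemia" and a high-side term. The row below (sodium) has "Hyponatremia" and a high-side term. Glucose also has both.

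SAP 8.10.2 says that all laboratory values will receive a CTCAE v5 severity grade, that newly occurring grade 3 or 4 values form the notable-abnormality listing, and that shift tables will run from baseline to the worst later grade. It adds: "Note that for parameters with two directions abnormalities (hypo/hyper), two tables will be presented". Protocol 9.4.1 carries the same rule.

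Potassium is collected. The biochemistry panel in Protocol 6.2.1 includes "electrolytes (sodium, potassium, magnesium and bicarbonates" among its tests.

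**The concern.** Potassium can be abnormal in either direction, and the SAP treats the two neighbouring electrolytes that way. Nothing in the SAP explains why potassium should be graded on the high side only, and no low-potassium term appears anywhere else in the SAP text.

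Appendix 3 is the only place where the SAP sets out which parameters are graded and in which direction, so it is the natural source for a programmer. Used that way, it supplies no term, and hence no grade, for a low value. Both the shift table and the notable-abnormality listing are built on the grade. Safety is the trial's primary objective, and SAP section 4 reports that the study stopped with 6 treated patients, so the safety outputs carry most of the report.

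**Working it through.** There is no sample size or power figure to reproduce (SAP 7.1: "No formal sample size calculation is planned for this study"). The check is a count of the appendix rows and a trace of what depends on them.

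**Step 1. Count Appendix 3 by direction.**

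| Terms given | Parameters | Count |
|---|---|---|
| Low and high | hemoglobin, leukocytes, lymphocytes, glucose, magnesium, sodium | 6 |
| Low only | neutrophils, platelets | 2 |
| High only | ALT, AST, total bilirubin, alkaline phosphatase, creatinine, potassium | 6 |

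Total parameters: 6 + 2 + 6 = 14. Low-side terms: 6 + 2 = 8. High-side terms: 6 + 6 = 12. Graded parameter-directions: 8 + 12 = 20.

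The other five high-only rows are liver tests and creatinine. Potassium is the only electrolyte in that group.

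**Step 2. Count after adding a low-side potassium term.** Two-direction parameters: 6 + 1 = 7. Low-side terms: 8 + 1 = 9. Parameter-directions: 20 + 1 = 21. All three electrolytes in the appendix would then be graded both ways.

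**Step 3. Trace a low potassium value through the SAP.**

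- Grade: SAP 7.6.2 gives grade 0 to values inside the normal range, including where a local normal range overlaps a non-zero grade. It sets the grade to missing only where normal limits are needed and absent. A value below a known lower limit meets neither rule, and Appendix 3 offers no low-side term. Under the appendix the grade is therefore undefined.
- Shift table: Table 14.3.4.2.2 compares baseline grade with worst grade. With no low-side grade, there is no low-direction table for potassium.
- Notable listing: Table 14.3.4.1 takes grades 3 and 4. An ungraded value cannot enter it.
- Raw listing: Listing 16.2.8.2 shows biochemistry values whether graded or not, so the value is still there.
- Adverse events: under Protocol 8.2.5, a treatment-emergent abnormality that comes with symptoms, changes study medication or needs treatment or clinical management is recorded as an adverse event. Protocol 8.2.2.4 grades that event by CTCAE. It then appears in Table 14.3.1.3 and, at grade 3 or 4, in Table 14.3.2.5.

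**Step 4. What is left uncovered.** A low potassium that meets none of the three conditions in Protocol 8.2.5 would appear only as an ungraded raw value.

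**Step 5. Could the body text settle it?** SAP 8.10.2, read alone, points to grading both directions. It cannot be taken as literally covering every test, because red cell count and bicarbonate are collected but have no row in Appendix 3. It also ties the scope of the shift tables back to what the SAP itself specifies. The two places give a programmer different answers.

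**The case against.** The strongest reply is that 8.10.2 already gives the right instruction. It requires all values to be graded and two tables for two-direction parameters, and neither 8.10.2 nor 7.6.2 cites Appendix 3 or restricts grading to its rows. (SAP 6.2, by contrast, does cite Appendix 1.) A programmer following the body text would handle low potassium correctly. This stands in part: it turns the point into a conflict between body and appendix, and the omission becomes conditional on the appendix being used as the specification.

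A second reply is that the table was read from a PDF and a cell may have been lost. That cannot be excluded. It is unlikely, because the high-side term sits in its proper column, every two-direction row is intact, and the other blanks fall where one would expect.

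A reader might infer more than the documents support:

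- *That low potassium would never be graded or listed.* The body text calls for grading, and the raw values are listed in any case.
- *That low values would be coded grade 0.* Section 7.6.2 does not assign grade 0 to a value below normal.
- *That the information is lost at every visit.* Raw values remain for each assessment, and clinically significant ones become graded adverse events, which are the stated primary endpoint.
- *That the effect can be put at 16.7 percentage points.* This is only 1/6, and holds for any event in one of six patients. The documents give no rate or observed value for low potassium.

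**Conclusion.** Appendix 3 and SAP 8.10.2 are inconsistent on potassium. The likely explanation is a clerical blank. If outputs follow the appendix, one direction of one of 14 parameters drops out of two outputs, Tables 14.3.4.1 and 14.3.4.2.2. With six treated patients, the raw listing can be read by eye, so the practical effect is small. The documents do not allow an estimate of how many patients, if any, would be affected.

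The conclusion rests on two assumptions: that the blank cell is in the source document, and that Appendix 3 is used as the grading specification, as its title suggests. It is a minor point, worth correcting because it touches a safety output and costs almost nothing.

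**What to change.** 1. Check the source PDF to confirm that the low-side potassium cell is empty there.
2. If it is, enter the CTCAE v5.0 low-potassium term in that cell of Appendix 3.
3. Produce low-direction and high-direction shift tables for potassium under Table 14.3.4.2.2, in line with 8.10.2, and let low-side grade 3-4 values feed Table 14.3.4.1.

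The cost is one table cell and one extra shift table. Potassium is already collected, so no new data are needed.
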